### 4.1.6 Packaging, labelling and re-supply

Boehringer Ingelheim will provide all study supplies including blinded study medication, rescue medication and Respimat® inhaler training kits. Expiry date will be pre-printed on the trial supplies labels.

**Proprietary confidential information.**

© 2015 Boehringer Ingelheim International GmbH or one or more of its affiliated companies. All rights reserved.

This document may not - in full or in part - be passed on, reproduced, published or otherwise used without prior written permission.

Open-label supplies= Non Investigational Medicinal Product (NIMP)

- Training Respimat® inhaler, placebo cartridges and disposable mouthpieces for training purposes. A training device may be used for more than one training session. The training Respimat® can be used until 3 months after first insertion of the cartridge or until the device is empty. The date of the cartridge insertion should be entered on the medication label of the Respimat® immediately after the cartridge is inserted. A new mouthpiece should be used for each patient.

Respimat® inhaler and disposable mouthpieces for training purposes will be provided by IRT along with the initial supply order.

- Salbutamol (albuterol\*) HFA MDI inhalation aerosol (100 µg per actuation) for use as rescue medication during screening, treatment and follow-up periods. The rescue medication will be provided by BI and purchased locally.
- Salbutamol (albuterol\*) HFA MDI inhalation aerosol (100 µg per actuation) will also be used for qualifying PFT at Visit 1 (+4/\*,5%(\*6+-A2+(-=69

*\* NOTE: Albuterol sulphate is the official generic name in the US and salbutamol sulphate is the WHO recommended generic name.*

Blinded study medication= Investigational Medicinal Product (IMP)

- Packaging: the Respimat® treatment box will contain one Respimat® inhaler plus one drug-filled cartridge and contains sufficient medication for 30 days of treatment. The Respimat® inhaler will lock after 60 actuations have been administered and will no longer actuate any medication.
- Labelling: individual Respimat® treatment box will have a three-part tear-off label. One part of each tear-off label should be attached to the drug accountability form which will be part of the ISF, and one part will remain on the box (an extra part is available as well). The investigator or designee should fill out the following information:
  - date of cartridge insertion should be entered at time of cartridge insertion on the cover page of the cartridge booklet
  - Investigator's name should be entered at time of dispense on the cover page of the booklet on the Respimat® treatment box.

For details of the packaging and the description of the label, refer to the ISF.

#%Q+-44'6

Each site will receive a first supply at or after the initiation visit and will be resupplied upon demand by IRT.

#### 4.1.7 Storage conditions

All clinical trial supplies must be stored in a locked, secure cabinet and must be kept in their original packaging under the recommended storage conditions and may only be dispensed to trial subjects according to protocol. A temperature log must be maintained to assure that the drug supplies are stored at the correct temperature.

**Proprietary confidential information.**

© 2015 Boehringer Ingelheim International GmbH or one or more of its affiliated companies. All rights reserved.

This document may not - in full or in part - be passed on, reproduced, published or otherwise used without prior written permission.

The Respimat® inhaler and cartridges should be stored as indicated on the country specific booklet page. A temperature log must be maintained at the site to make certain that the drug supplies are stored at the correct temperature. If the storage conditions are found to be outside the specified range, immediately contact the local clinical monitor.

Further details are provided in the IB and on the country-specific labels, a sample of which will be part of the ISF.

#### 4.1.8 Drug accountability

The investigator / pharmacist / investigational drug storage manager will receive the investigational drugs delivered by the sponsor when the following requirements are fulfilled:

- approval of the study protocol by the IRB / ethics committee,
- availability of a signed and dated clinical trial contract between the sponsor and the Head of Trial Centre,
- approval/notification of the regulatory authority, e.g. competent authority,
- availability of the curriculum vitae of the principal investigator,
- availability of a signed and dated clinical trial protocol or immediately imminent signing of the clinical trial protocol, in exceptional cases, medication could already be sent to the site, before its activation via IRT.
- if applicable: availability of the proof of a medical licence for the principal investigator,
- for USA availability of the Form 1572.

The investigator / pharmacist / investigational drug storage manager must maintain records of:

- the product's delivery to the trial site,
- the inventory at the site,
- the use by each patient,
- the return to the sponsor or alternative disposition of used/unused trial medication.
- the adequate documentation that the patients were provided the doses specified by the CTP
- the reconciliation of all investigational products received from the sponsor

At the time of return to the sponsor, the investigator and/or pharmacist and/or investigational drug storage manager must verify that all drug supplies used/ unused or partially used have been returned by the clinical trial patient and that no remaining supplies are in the investigator's possession.

The investigator/pharmacist will record on the drug accountability forms the following information.

#### Respimat® inhaler:

- dates (dispense and return),
- dispenser's initials,

**Proprietary confidential information.**

© 2015 Boehringer Ingelheim International GmbH or one or more of its affiliated companies. All rights reserved.

This document may not - in full or in part - be passed on, reproduced, published or otherwise used without prior written permission.

- batch/serial numbers,
- expiry dates,
- the unique RespiMat® treatment box number assigned by IRT,
- trial patient number assigned by the RDC system.

See [Section 4.1.2](#). It is important to enter the date of priming on the medication label of the RespiMat®.

#### Rescue medication:

One NIMP accountability form will be provided for salbutamol to the trial site. This record will include:

- dates (dispense and return)
- dispenser's initials
- quantities,
- batch/serial numbers,
- expiry date,
- the trial patient number assigned by the RDC system.

The patient will be asked to return all used/unused rescue medication inhalers at each clinic visit. Source data documentation and full drug accountability in regard to dispensed and returned medication to investigational site and to patients are required. Only used inhalers will be replaced at each clinic visit. For further details, please refer to [section 4.2.1](#) (Rescue medication).

## **4.2 CONCOMITANT THERAPY, RESTRICTIONS, AND RESCUE TREATMENT**

### **4.2.1 Rescue medication, emergency procedures, and additional treatments**

#### 4.2.1.1 Rescue medication

Patients could use the open-label salbutamol /albuterol\* inhalation aerosol (HFA-MDI) for p.r.n use as needed for symptom relief. Administration of rescue medication can occur at any point during the trial as deemed necessary by the patient or the investigator.

Rescue medication will be issued to all patients at the screening visit (Visit 1) and can be dispensed at any time during the study until the follow-up Visit. It is important to provide sufficient rescue medication inhalers to cover the period between 2 clinic visits (3 months).

Rescue medication training and testing: please refer to [section 4.1.4.3](#)

Rescue medication supply: please refer to [section 4.1.6](#)

Rescue medication accountability: please refer to [section 4.1.8](#)

#### 4.2.1.2 Emergency procedures

There are no special emergency procedures to be followed.

#### 4.2.1.3 Additional treatments

In the case of COPD exacerbations, investigators are allowed to prescribe whatever COPD medication they deem appropriate for the patient.

The use of antibiotics is not restricted and may be prescribed as medically necessary for exacerbations and / or infections.

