**Proprietary confidential information.**

© 2015 Boehringer Ingelheim International GmbH or one or more of its affiliated companies. All rights reserved.

This document may not - in full or in part - be passed on, reproduced, published or otherwise used without prior written permission.

Women of childbearing potential may be included in clinical trials for tiotropium + olodaterol (5/5 µg) FDC provided appropriate precautions are taken to minimize the risk of pregnancy. These precautions include pregnancy testing and use of a highly effective method of birth control. Continued testing and monitoring during the trial should be sufficient to ensure compliance with the measures not to become pregnant during the period of drug exposure (which may exceed the length of study until the follow-up visit at 21 days after discontinuation of study medication) [[R05-0370](#)].

The trial design requires that patients will be randomized at Visit 2 (1:1) to one of the following treatments:

- i. Tiotropium + olodaterol FDC (2.5 µg / 2.5 µg per actuation) inhalation solution
- ii. Tiotropium (2.5 µg / per actuation) inhalation solution (control group)

There is no placebo comparator in this trial.

Patients taking commercial tiotropium with/without LABAs will take their maintenance treatment up to the day prior to the randomization visit (visit 2).

Patients receiving inhaled corticosteroids before enrolment will continue their treatment (or the inhaled corticosteroids component alone if taken as a fixed combination with bronchodilator) at the same equivalent dose and regimen during the study. The only medications that are excluded during the treatment period are anticholinergic and long-acting β-adrenergic other than the study drugs.

The proposed medication restriction scheme is considered ethically acceptable given the availability of rescue SABA and permitted use of other maintenance medications in conjunction with close clinical monitoring for exacerbation symptoms.

During the whole course of the trial Boehringer Ingelheim will provide open-label salbutamol/albuterol HFA MDI to be used as rescue medication for all patients after they have signed their informed Consent.

Safety will be monitored (as described in [Section 5.2](#)) at site visits and at each telephone contact alike. Patients will be contacted by site staff and asked for COPD exacerbation status, adverse events and change in concomitant therapy.

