#### Please note

1. A patient should not be withdrawn from the trial because he/she experiences a COPD exacerbation during the treatment period.
2. If during the treatment period, the trial medication is for any reason (e.g. hospitalisation stay) interrupted more than 14 consecutive days, a discussion with the clinical monitor is required to re-assess the patient's participation in the study.

Refer to [Section 6.2.3](#) for procedures to be followed for patients prematurely terminating the trial.

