### 4.2.2 Restrictions

#### 4.2.2.1 Restrictions regarding concomitant treatment

The following table provides an overview of permitted and restricted medication over the different study periods. The COPD maintenance therapy including long-acting anticholinergic, inhaled corticosteroids and long-acting  $\beta$ -adrenergic drugs given either alone or in combination should be discussed at Visit 1 in order to adapt optimal treatment management in tune with the [Table 4.2.2.1:1](#) (Permitted Medications and Medication Restrictions).

Patients receiving corticosteroids at baseline (inhaled corticosteroid component alone if taken as fixed combination with a bronchodilator) will continue treatment at the same dose or equivalent dose and regimen during their treatment period. If the patient withdraws from the treatment period, the dual ICS/LABA could be resumed.

[figure not shown]
Please refer to [Section 3.3.4.1](#) (Removal of individual patients).

ICS mono-product adjustment is allowed during COPD exacerbation and should be linked to the reported exacerbation event.

Proprietary confidential information.

© 2015 Boehringer Ingelheim International GmbH or one or more of its affiliated companies. All rights reserved.

This document may not - in full or in part - be passed on, reproduced, published or otherwise used without prior written permission.

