**Proprietary confidential information.**

**© 2015 Boehringer Ingelheim International GmbH or one or more of its affiliated companies. All rights reserved.**

This document may not - in full or in part - be passed on, reproduced, published or otherwise used without prior written permission.

Table 4.2.2.1: 1 Permitted Medications and Medication Restrictions

Drug Class	Sub-class	Prior to study	Study Period		
			Screening Period	Treatment Period	Follow up Period
Corticosteroids	Inhaled corticosteroids (iCS) (stabilized 4wks prior to V1)	Permitted 	Permitted 	Permitted 	Permitted 
	Oral corticosteroids [≤10 mg prednisone per day or ≤20 mg prednisone every other day (or equivalent); stabilized 4 wks prior to V1]	Permitted	Permitted	Permitted	Permitted
	Injected corticosteroids local administration (e.g. bursitis)	Permitted	Permitted	Permitted	Permitted
	Nasal corticosteroid sprays	Permitted 	Permitted 	Permitted 	Permitted 
β-adrenergics	Inhaled short-acting β-adrenergics (SABA)	Permitted	Rescue medication (as supplied) only 	Rescue medication (as supplied) only 	Rescue medication (as supplied) only 
	Inhaled long-acting β-adrenergics (bid) (LABA) (e.g. formoterol / salmeterol)	Permitted	Permitted 	NOT permitted	Permitted
	Inhaled long-acting β-adrenergics (qd) (e.g. indacaterol, vilanterol)	Permitted	Permitted 	Study medication ONLY permitted	Permitted
	Oral and patch beta-adrenergics	NOT permitted	NOT permitted		Permitted
	Beta blockers (stabilized 6 wks prior to V1)	Permitted	Permitted	Permitted	Permitted
Anticholinergics	Short-acting anticholinergics (e.g. inhalation aerosol, nasal spray)	Permitted	Permitted 	NOT permitted	Permitted
	Long-acting anticholinergics (bid/qd) (e.g: commercial tiotropium, umeclidinium aclidinium, glycopyrronium)	Permitted	Permitted 	Study medication ONLY permitted	Permitted

Table 4.2.2.1: 1 Permitted Medications and Medication Restrictions (cont'd)

Drug Class	Sub-class	Prior to study	Study Period		
			Screening Period	Treatment Period	Follow up Period

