## 5.1.2 Assessment of efficacy

### 5.1.2.1 Definition of moderate and severe COPD exacerbations

For the purpose of this study, a COPD exacerbation is defined as a complex of lower respiratory events / symptoms (increase or new onset) related to the underlying COPD, with duration of three days or more, requiring a prescription of antibiotics and / or systemic steroids and/or hospitalisation.

A complex of lower respiratory events / symptoms is defined as at least two of the following:

- Shortness of breath
- Sputum production (volume)
- Change in sputum colour
- Cough
- Wheezing
- Chest tightness

“Onset of exacerbation” will be defined by the onset of first recorded symptom. The “end of exacerbation” will be decided by the investigator based on clinical judgment.

Exacerbations will be classified as follows:

- Mild: a new prescription of maintenance bronchodilator only
- Moderate: patient receiving an exacerbation-related prescription of oral corticosteroids and/ or antibiotic not requiring hospitalisation.
- Severe: COPD-related hospitalisation including emergency room visit\*

To consider hospitalisation associated with COPD exacerbation, the information collected should include the start date of all COPD-related hospitalisations as well as the discharge date from the hospital or equivalent

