## 6.2 IMPORTANT PROTOCOL VIOLATIONS

A patient’s deviation from the trial protocol is considered “important” if it can be expected that the deviation had a distorting influence on the assessment of the treatment effect on the primary endpoint of the trial or could affect the patient’s safety/rights.

If the Interactive Response Technology (IRT)-assigned randomized medication is not available at the site at the first visit, a forced randomization will occur, and the IRT will assign a treatment that is available at the site. That patient will be assigned within the IRT system to receive that same treatment for the remainder of the trial. Forced randomizations

are part of the study plan and are not classified as important protocol violations. The number of forced randomizations will be closely monitored and described in the clinical trial report.

Table 6.2: 1 Important protocol violations

Category/ Code	Description	Example/Comment	Excluded from	Automatic /Manual
A	Entrance criteria not met			
A1	Inclusion criteria not met	IC 3, 4, 5, 7, 8, 2, 6,	None	Automatic and manual
A2	Exclusion criteria not met	EC 3, 7, 9, 10, 11, 13, 14, 15, 17, 23, 5, 6, 1, 4, 8, 2, 12, 16, 18, 19, 20, 21, 22	Excluded from TS: EC 22 Excluded from none: EC 1-21, 23	Automatic
B	Informed consent			
B1	Informed consent to study not available/not done*		All	Manual
B2	Informed consent too late**		None	Manual
C	Trial medication and randomization			
C1	Incorrect trial medication taken		None	Manual
C2	Randomization order not followed	Date of first trial drug intake prior to randomization date	None	Automatic
C3***	Serious non-compliance with study medication as reported in monitoring report	Decision at BRPM/MQRM.	None	Manual
C4	Medication code broken inappropriately		None	Manual
D	Concomitant medication			
D2	Prohibited medication use during study	Refer to Table 4.2.2.1: 1 in revised CTP.	None	Manual
Z	Other			
Z1	Serious Good Clinical Practice (GCP) non-compliance	Manual PVs reported by CML/CRA or in the GEM system.	None	Manual
Z2	Other PV affecting efficacy and possibly safety		None	Manual

\* Informed consent date missing; no signature on ICF.

\*\* Applies to all informed consents. Date of informed consent was after the date of any study-related procedure.

\*\*\* “Serious non-compliance with study medication” is defined by compliance  $\geq 200\%$  (twice the dose or more).

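### Section 4.2.1.3 allows any COPD medication for an exacerbation, while Table 4.2.2.1:1 and section 2.3 bar non-study LABA and anticholinergics in the treatment period; the passages must be reconciled, because later events still count

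*Protocol*

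**What the plan says.** Protocol section 4.2.1.3 (Additional treatments) states: "In the case of COPD exacerbations, investigators are allowed to prescribe whatever COPD medication they deem appropriate for the patient". It names no drug class, duration or return to prior therapy.

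Table 4.2.2.1:1 governs the treatment period. It does not permit twice-daily LABA, ICS/LABA, LAMA/LABA, short-acting anticholinergics or PDE-4 inhibitors. For once-daily LABA and for long-acting anticholinergics the entry is "Study medication ONLY permitted". None of these rows carries an exacerbation exception. The text of section 4.2.2.1 gives one: "ICS mono-product adjustment is allowed during COPD exacerbation and should be linked to the reported exacerbation event". The same section ties resumption of ICS/LABA to withdrawal from the treatment period.

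Section 2.3 gives a shorter list: "The only medications that are excluded during the treatment period are anticholinergic and long-acting β-adrenergic other than the study drugs". The table also bars PDE-4 inhibitors, oral and patch beta-adrenergics, and antibiotics used to prevent exacerbations.

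Section 3.3.4.1 adds: "A patient should not be withdrawn from the trial because he/she experiences a COPD exacerbation during the treatment period". Section 5.1.2.1 classifies severity and includes "Mild: a new prescription of maintenance bronchodilator only".

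In the SAP, Table 6.2:1 lists D2, "Prohibited medication use during study", by reference to the protocol table, and excludes such patients from no analysis. Section 6.3 defines no per-protocol set. Sections 6.1 and 7.4 count every moderate or severe exacerbation from first dose to last dose plus one day.

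**The concern.** A LABA added to tiotropium is the randomised contrast. If open-label LABA is started after a first exacerbation while study drug continues, a Tio 5 patient is from then on treated with tiotropium plus a drug of the same class as olodaterol, and a T+O patient with two LABAs. The table bars both situations; section 4.2.1.3, read literally, allows both. Second and later events enter the primary count unchanged, so any benefit of the added LABA in the Tio 5 arm narrows the observed difference.

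Two practical problems follow. Sites that work from the table and sites that work from 4.2.1.3 can act differently, in a trial planned for more than 50 countries. It is also unclear whether a LABA given under 4.2.1.3 is a D2 violation, so the violation listing may not measure the extent of use consistently.

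The primary rate is the endpoint mainly affected. Time to first moderate or severe exacerbation could be reached only by a LABA started earlier, for instance for a mild exacerbation.

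**Working it through.** **Do the passages conflict under a narrower reading?** One might take 4.2.1.3 to mean acute treatment of the episode only. The conflict remains, because the table also bars short-acting anticholinergics during treatment and limits short-acting beta-agonists to the supplied rescue inhaler. The severity definition in 5.1.2.1 also shows that a new maintenance bronchodilator is a foreseen response to an exacerbation, although that definition grants no permission.

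**Inputs (protocol section 7.6).** Tio 5 rate 0.85 per year; T+O rate 0.748; rate ratio 0.88; two-sided alpha 0.01; dispersion k from 0.625 to 0.9; 3900 per arm; 15% loss of patient-years, taken as t = 0.85 year per patient.

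**Reproducing the plan.** n per arm = (2.576 + 1.282)² × [1/0.85 + 1/0.748 + 2k] / (ln 0.88)². For k = 0.625, 0.7, 0.8 and 0.9 this gives 3426.7, 3563.3, 3745.4 and 3927.5, against 3427, 3563, 3745 and 3927 in Table 7.6:1.

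Power after the 15% loss = Φ(|ln RR| / SE − 2.576), with SE² = (1/m₀ + 1/m₁ + 2k) / 3900, m₀ = 0.85 × 0.85 = 0.7225 and m₁ = 0.748 × 0.85 = 0.6358.
- k = 0.625: SE = √(4.2069/3900) = 0.03284; 0.1278/0.03284 − 2.576 = 1.316; power 90.6%.
- k = 0.9: SE = √(4.7569/3900) = 0.03492; 0.1278/0.03492 − 2.576 = 1.084; power 86.1%.

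Both equal the stated range of 86.1% to 90.6%.

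**Events open to dilution, on the same 0.85-year basis.** P(at least one event on Tio 5) = 1 − (1 + k·m₀)^(−1/k). Second and later events per patient: R = m₀ − P.
- k = 0.625: P = 0.449; R = 0.273; share 0.273/0.7225 = 38%.
- k = 0.9: P = 0.427; R = 0.296; share 0.296/0.7225 = 41%.

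**Illustration.** Assume that a share p of Tio 5 patients with a first event starts a LABA at once, keeps it, and has a later rate multiplied by 0.88; that T+O patients gain nothing from a second LABA; and that k is unchanged. Then m₀(p) = 0.7225 − 0.12 × p × R, and RR(p) = 0.6358 / m₀(p).

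| p | m₀(p), k = 0.625 / 0.9 | Rate ratio | Power, k = 0.625 / 0.9 |
|---|---|---|---|
| 0 | 0.7225 / 0.7225 | 0.880 | 90.6% / 86.1% |
| 10% | 0.7192 / 0.7190 | 0.884 | 88.0% / 82.7% |
| 20% | 0.7159 / 0.7154 | 0.888-0.889 | 84.9% / 78.7% |
| 50% | 0.7061 / 0.7048 | 0.900-0.902 | 72.7% / 64.1% |

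Worked cell (p = 50%, k = 0.625): 0.7225 − 0.12 × 0.5 × 0.2734 = 0.7061; RR = 0.6358/0.7061 = 0.9004; SE = √(4.2391/3900) = 0.03297; 0.1049/0.03297 − 2.576 = 0.605; power 72.7%.

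For its time-to-first-event calculation, section 7.6 assumes that 65% of Tio 5 patients have an event within a year. That figure would leave only (0.85 − 0.65)/0.85 = 24% of events as second or later, and the shifts would be smaller.

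**The case against.** The strongest reply is that the documents lean towards the ban. Section 4.2.1.3 sits among rescue and additional treatments and is followed at once by the restrictions. Section 4.2.2.1 asks that maintenance therapy follow the table, relaxes only mono-product ICS and links ICS/LABA to withdrawal. Section 2.3 also excludes non-study LABA, and D2 refers to the table. On that view one general sentence stands against several specific ones, and continued LABA use is a recorded violation. This stands as a guide to probable intent. It does not remove the contradiction, since no text says that 4.2.1.3 is subject to the table.

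Other parts of the reply also stand:
- Counting events after such use is a defensible treatment-policy choice; the visible text simply does not state it as one.
- Opportunity is nearly balanced: with the design inputs, 47-49% of Tio 5 and 44-46% of T+O patients have an event within 12 months. The dilution comes from assuming benefit in Tio 5 and none in T+O.
- SAP section 7.2 already summarises concomitant therapy during treatment by arm, which may give part of the count.
- A block in section 4.2.2.1, just before its reference to removal of patients, is not visible, nor are parts of the SAP.

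A reader might infer that Tio 5 patients can receive the tested add-on itself. The documents do not support this: no passage offers open-label olodaterol, and what 4.2.1.3 opens is a drug of the same class. A reader might also infer that the SAP has no analysis for this. The visible sensitivity analysis, over the planned treatment period, extends the window past discontinuation and does not address LABA taken on study drug, but hidden text could.

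**Conclusion.** The contradiction is real and bears on the primary endpoint, because patients continue on study drug and their later events count. Section 2.3 is also narrower than the table it should match. The direction of any effect is towards no difference, so the issue is power and interpretation: a null result could not readily be told apart from dilution. No false-positive risk is shown.

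The size is unknown. The loss ranges from about 3 points of power at p = 10% to about 18-22 points at p = 50%, and these figures rest wholly on an assumed p, persistent use and the full 12% benefit. They should not be read as a forecast that the trial is underpowered; the documents give no rate of use. Given the low cost of a correction, the sponsor should make it.

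**What to change.** 1. Reconcile protocol sections 4.2.1.3 and 2.3 with Table 4.2.2.1:1, so that one statement governs medication given for an exacerbation while study drug continues. Word D2 in SAP Table 6.2:1 to match. Which rule applies is for the sponsor to decide.
2. In the SAP, tabulate by arm the patients who take a non-study LABA or long-acting anticholinergic while on study drug. SAP section 7.2 may need only a more specific row.
3. Confirm whether start dates of these drugs are captured. Protocol section 5.4 has therapies entered on the Concomitant Therapy eCRF, but SAP section 7.2 describes checkbox collection, so dates cannot be presumed. Only if dates exist, add to SAP section 7.4 a supportive analysis with the same negative binomial model that ends counted events and exposure at the start of the non-study drug. State that stopping at a drug prompted by an exacerbation may be informative.

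The primary analysis stays unchanged. The cost is a protocol wording change, one table and, conditionally, one supportive model.
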